4.3 Follow-up period (Not applicable)

5. STUDY ASSESSMENTS

The Investigator will ensure that data are recorded in an appropriately designed excel data sheet and will ensure the accuracy, completeness, and timeliness of the data collection.

5.1 Efficacy assessments

Study outcome measures are summarized in Section 8.4.

5.1.1 HbA1c

Blood samples for measurement of HbA1c will be collected according to the schedule presented in the Study Plan (Table 1). The instructions for collection, processing, packaging, and shipping of the samples will be detailed in the laboratory manual.

5.1.2 Fasting plasma glucose

Blood samples for measurement of FPG will be collected according to the schedule presented in the Study Plan (Table 1). The instructions for collection, processing, packaging, and shipping of the samples will be detailed in the laboratory manual.

5.1.3 Body weight

Body weight will be measured according to the schedule presented in the Study Plan (Table 1). The study site staff should record the weight in kilograms or pounds to the first decimal point (e.g., 95.3 kg). The same scale should be used and the patient should wear a standard hospital-type gown or equivalent light clothing and no shoes for the body weight measurement at each visit.

5.1.4 Body height

Body height will be measured according to the schedule presented in the Study Plan (Table 1). The study site staff should record the height in centimeters. The patient should remove their footwear and head gear and stand with feet together, heels against the back board, and knees straight.

5.1.5 Waist and hip circumference

For waist and hip circumference measurement, the study site personnel must ensure that:

- The patient stands and the examiner places a Gulick II measuring tape in a horizontal plane around the abdomen at the level of the umbilicus for waist circumference and at the maximum circumference of the buttocks for hip circumference.
- The measuring tape is snug, but does not compress the skin, is parallel to the floor, and is not twisted.
- The measurement is taken at the end of a normal respiratory expiration.
- The measurement is recorded in centimeters to the first decimal point.
- Waist and hip circumference will be measured according to the schedules presented in the Study Plan (Table 1).

5.1.6 7-point self-monitored blood glucose profiles

Patients will be instructed to perform 7-point SMBG profiles at home on the same day of the week (± 2 days), the week before Visits 3, 4, 5, 6, 7, and 8 (Table 1). A 7-point SMBG profile consists of blood glucose measurements obtained prior to and 2 hours after the morning, midday, and evening meals, and before bedtime.

The 7-point SMBG should not be performed the day immediately before Visits 3 and 7.

5.1.7 Dual Energy X-ray Absorption (DEXA) scan

Patients will be assessed for percent body fat with a DEXA scanner at Visits 1 and 8 (Table 1). A complete DEXA scan report will be kept as source documentation.

5.1.8 Glucose turnover study

A glucose turnover study will be performed according to schedule presented in Table 1. A glucose turnover study will be performed at Visit 3, which should be 5 to 14 days after the OGTT (Visit 2). An end of treatment glucose turnover study will be performed at Visit 7 and should be done approximately 10 days prior to the OGTT.

Patients will report to the study site after a 10-hour overnight fast and should be asked to void before beginning the glucose turnover study. At approximately 0600 (Time -180 minutes), a catheter will be placed into an antecubital vein and a primed (25 micro Curie [μCi] x FPG/100 up to a maximum of 50 μCi) – continuous infusion of [$3\text{-}^3\text{H}$]-glucose will be started]. The continuous infusion (0.25 $\mu\text{Ci}/\text{min}$) of [$3\text{-}^3\text{H}$]-glucose will be started and will be maintained throughout the study duration. A second catheter will be placed retrogradely into a vein on the dorsum of the hand, which will be placed in a heated box (50-60°C) for arterialized blood withdrawal. Prior to oral administration of study medication (saxagliptin, dapagliflozin, placebo), blood samples will be taken at the timepoints indicated in Table 3 for measurement of plasma glucose, insulin, C-peptide, glucagon, counter-regulatory hormones (i.e., plasma cortisol, growth hormone, adrenaline, and noradrenaline), and [$3\text{-}^3\text{H}$]-glucose specific activity. During the glucose turnover study, patients will receive assigned study medication 3 hours after the start of [$3\text{-}^3\text{H}$]-glucose infusion (Time 0). Blood samples will be obtained according to the timepoints indicated in Table 3 until the end of the study (Time 300 minutes/5 hours after drug is received). Metformin or metformin/sulfonylurea will **NOT** be taken until after the glucose turnover study has been completed.

Urine will be collected from the start of the study (Time -180 minutes) until Time 0 and again from Time 0 to 300 to measure urinary volume and urinary glucose concentration (to quantitate urinary glucose excretion). The glucose turnover study will end 5 hours after receiving study medication (Time 300 minutes) and patients will be given a meal and metformin or metformin/sulfonylurea and allowed to return home.

Table 3 Glucose Turnover Study

Timepoint (clock time)^a	Glucose	3-³H-glucose	Insulin/ C-peptide	Glucagon	CR hormones^b
-180 (0600)	X	X			
-30	X	X	X	X	X
-20	X	X			
-10	X	X	X	X	X
-5	X	X			
0 (0900) ^c	X	X	X	X	X
15	X	X	X	X	
30	X	X	X	X	X
45	X	X	X	X	
60 (1000)	X	X	X	X	X
75	X	X	X	X	
90	X	X	X	X	
105	X	X	X	X	
120 (1100)	X	X	X	X	X
135	X	X	X	X	
150	X	X	X	X	
165	X	X	X	X	
180 (1200)	X	X	X	X	X
195	X	X			
210	X	X	X	X	
225	X	X			
240 (1300)	X	X	X	X	X
255	X	X			
270	X	X	X	X	
285	X	X			
300 (1400)	X	X	X	X	X
Number of samples	26	26	19	19	9

^a Study start time is approximate (between 0600 and 0700), but collection of samples relative to time of study medication ingestion is critical (i.e., -180, -30, -20 minutes, etc.).
 
^b CR counter-regulatory hormones include: plasma or serum cortisol, growth hormone, adrenaline, and noradrenaline.
 
^c During Visit 3 glucose turnover study, patient will perform some Visit 3 assessments during the 3 hour priming period and be randomized prior to Time 0 then receive assigned study medication at Time 0.
					

5.1.9 Double tracer oral glucose tolerance test

An OGTT will be performed according to the schedule presented in [Table 1](#), which will occur 5 to 14 days prior to a glucose turnover study.

Patients will report to the clinic after a 10-hour overnight fast and should be asked to void before beginning the double tracer OGTT study. At approximately 0600 hours, a catheter will be inserted into an antecubital vein, and primed (25 μCi x FPG/100 up to maximum of 50 μCi) – continuous infusion of $3\text{-}^3\text{H}$ -glucose will be started. The continuous (0.25 $\mu\text{Ci}/\text{min}$) infusion of [$3\text{-}^3\text{H}$]-glucose will be started 3 hours (Time -180 minutes) prior to administering glucose challenge and will be maintained for the entire study duration (7 hours). A second catheter will be placed retrogradely into a vein on the dorsum of the hand, which will be placed in a heated box (50-60°C) for arterialized blood withdrawal. Prior to glucose challenge, blood samples will be taken at time points indicated in [Table 4](#) for measurement of FPG, insulin, C-peptide, glucagon, FFA, GLP-1, and GIP concentrations and plasma ^3H -glucose and ^{14}C -glucose specific activities. Three hours after the start of [$3\text{-}^3\text{H}$]-glucose infusion (Time 0), patients will receive 75 grams of glucose containing 100 μCi $1\text{-}^{14}\text{C}$ -glucose orally. Blood samples will be collected at the time points indicated in [Table 4](#) until the end of the study (Time 240 minutes/4 hours after glucose challenge).

Urine will be collected from the start of the study (Time -180 minutes) until Time 0 and again from Time 0 to 240 to measure glucose and creatinine to account for urinary glucose loss following glucose ingestion. Rates of EGP, oral glucose appearance, and whole body glucose disposal will be calculated from ^3H -glucose and ^{14}C -glucose specific activities, as previously described ([Ferrannini et al 1985](#)). We have previously shown that 4 hours is sufficient for complete absorption of the ingested glucose load. Therefore, splanchnic (primarily reflects hepatic) glucose uptake will be determined as the ingested glucose load (75 grams) minus the amount of ^{14}C -glucose (integrated area from 0 to 240 minutes) that appears in the systemic circulation.

Table 4 Double Tracer Oral Glucose Tolerance Test

Timepoint (clock time) ^a	Glucose	Insulin	C-peptide	Glucagon	FFA	GIP/ GLP-1	$3\text{-}^3\text{H}$ -Glucose	$1\text{-}^{14}\text{C}$ -Glucose
-180 (0600)	X	Start $3\text{-}^3\text{H}$ -glucose infusion						X
-30	X						X	X
-20	X	X	X	X	X	X	X	X
-10	X	X	X	X	X	X	X	X
-5	X						X	X
0 (0900)	X	X	X	X	X	X	X	X
Ingest glucose (75 grams) containing 100 μCi $1\text{-}^{14}\text{C}$-glucose								

Timepoint (clock time) ^a	Glucose	Insulin	C-peptide	Glucagon	FFA	GIP/ GLP-1	3- ³ H-Glucose	1- ¹⁴ C-Glucose
15	X	X	X				X	X
30	X	X	X	X	X	X	X	X
45	X	X	X				X	X
60 (1000)	X	X	X	X	X	X	X	X
75	X	X	X				X	X
90	X	X	X	X	X	X	X	X
105	X	X	X				X	X
120 (1100)	X	X	X	X	X	X	X	X
135	X						X	X
150	X	X	X	X	X	X	X	X
165	X						X	X
180 (1200)	X	X	X	X	X	X	X	X
195	X						X	X
210	X	X	X	X	X	X	X	X
225	X						X	X
240 (1300)	X	X	X	X	X	X	X	X
Number of samples	22	15	15	11	11	11	21	22

Abbreviations: FFA free fatty acids, GIP glucose-dependent insulinotropic polypeptide, GLP-1 glucagon-like peptide-1.

^a Study start times are approximate (between 0600 and 0700), but timepoints relative to study start time are critical.

5.2 Safety assessments

The Investigator will evaluate all Screening and safety laboratory reports and will sign and date the review. Any out of range laboratory results should be assessed for clinical significance and reported as AEs accordingly. The Investigator should follow all clinically significant laboratory abnormalities occurring during the study that were not present at baseline. These abnormalities should be evaluated with additional tests, if necessary, until the underlying cause is diagnosed or resolution occurs.

Samples will be collected according to the schedules presented in the Study Plan ([Table 1](#)).

5.2.1 Laboratory safety assessments

Laboratory safety assessments will be performed as presented in the Study Plan ([Table 1](#)). Sample tubes and sample sizes may vary depending on laboratory method used and routine

practice at the site. Additional safety samples may be collected if clinically indicated at the discretion of the Investigator.

The Investigator should make an assessment of the available results with regard to clinically relevant abnormalities. The laboratory results should be signed and dated and retained at center as source data for laboratory variables.

5.2.1.1 Hematology

Hematology assessments (see [Table 5](#)) will include the following: red blood cell count, hemoglobin (Hb), hematocrit, white blood cell count, platelets, and differential counts.

5.2.1.2 Chemistry

Chemistry assessments (see [Table 5](#)) will include the following: creatinine, total bilirubin, alkaline phosphatase, AST, ALT, albumin, potassium, calcium, sodium, creatine kinase, chloride, bicarbonate, urea nitrogen, uric acid, magnesium, and phosphorus.

Table 5 Laboratory Variables

Hematology/Hemostasis (whole blood)	Clinical Chemistry (serum or plasma)
B-Hemoglobin (Hb)	S/P-Creatinine
B-Hematocrit	S/P-Bilirubin, total (TB)
B-Leukocyte count	S/P-Alkaline phosphatase
B-Leukocyte differential count (absolute count)	S/P-Aspartate transaminase (AST)
B-Platelet count	S/P-Alanine transaminase (ALT)
Urinalysis (dipstick)	S/P-Albumin
U-Hb/Erythrocytes/Blood	S/P-Potassium
U-Protein/Albumin/Creatinine	S/P-Calcium, total
	S/P-Sodium
	S/P-Creatine kinase
	S/P-Chloride
	S/P-Bicarbonate
	S-Urea nitrogen
	S/P-Phosphate
	S/P-Magnesium
	S/P-Uric acid

Abbreviations: AST aspartate transaminase, ALT alanine transaminase, B blood, U urine, Hb hemoglobin, P plasma, S serum, TB total bilirubin.

5.2.1.3 Urinalysis

Urinalysis assessments will be performed according to the Study Plan (Table 1) and will include the following: hemoglobin, erythrocytes, blood, protein, albumin, and creatinine.

5.2.1.4 Other clinical laboratory evaluations

Fasting lipid panel

Fasting serum lipids (total-cholesterol, LDL-cholesterol, HDL-cholesterol, non-HDL cholesterol, and triglycerides) will be assessed according to the Study Plan (Table 1).

Thyroid hormones

Blood samples will be collected for the measurement of TSH and T4 at Visit 1 (Screening), as presented in the Study Plan (Table 1). Patients with abnormal TSH or free T4 values will be excluded.

Pregnancy testing

All female patients, regardless of childbearing status (unless patient has had a hysterectomy), will provide urine or blood samples for pregnancy tests according to the schedule presented in the Study Plan (Table 1). The first dose of study medication or any other in-clinic dose of study medication will not be administered until a negative result is obtained.

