3.1 Inclusion criteria

For inclusion in the study, patients should fulfill the following criteria:

1. Provision of informed consent prior to any study-specific procedures.
2. Is able to read, understand, and sign the Informed Consent Forms (ICFs) and, if applicable, an Authorization to Use and Disclose Protected Health Information form (consistent with Health Insurance Portability and Accountability Act of 1996 legislation), communicate with the Investigator, and understand and comply with protocol requirements, including the use of diary and glucose meter measurements.
3. Age = 18-70 years.
4. Has a diagnosis of T2DM.
5. Has HbA1c $\geq 7.5\%$ and $\leq 11.0\%$ obtained at Screening.
6. Treated with a stable dose of metformin ≥ 1000 mg/day or stable dose of metformin (≥ 1000 mg/day) plus sulfonylurea (glipizide, ≥ 5 mg/day; glyburide, ≥ 5 mg/day; glimepiride, ≥ 4 mg/day) for at least 8 weeks prior to Screening.
7. Has a BMI of 20 to 45 kg/m² (inclusive) at Screening.
8. Is male, or is female, and meets all the following criteria:
 - Not pregnant or breastfeeding.
 - Negative pregnancy test result at Visit 1 (Screening).
 - Women of childbearing potential (WOCBP; [including perimenopausal women who have had a menstrual period within 1 year]) must practice and be willing to continue to practice appropriate birth control (defined as a method that results in a low failure rate, i.e., less than 1% per year, when used consistently and correctly, such as implants, injectables, hormonal contraceptives [pills, vaginal rings, or patches], some intrauterine contraceptive devices [levonorgestrel-releasing or copper-T], tubal ligation or occlusion, or a vasectomized partner) during the entire duration of the study. As applicable, all methods must be in effect prior to receiving the first dose of study medication.

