3.9.2 Procedures for discontinuation of a subject from investigational product

At any time, patients are free to discontinue IP or withdraw from the study (i.e., IP and assessments – see Section 3.10), without prejudice to further treatment. A patient who decides to discontinue IP will always be asked about the reason(s) and the presence of any AEs. If

possible, the patient will be seen and assessed by an Investigator(s). Any AEs will be followed up; patient diaries and all study drugs should be returned by the patient.

Patients who discontinue from the study medication will have an Early Termination Visit equivalent to the Week 16 assessments plus a glucose turnover study at the time of study medication discontinuation. The following data will be collected and entered onto the clinical database:

- Concomitant medication
- AEs

In the case of a decision to discontinue treatment, the Investigator will follow the patient until the event has resolved or stabilized, at least until Week 16.

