3.10 Criteria for withdrawal

Every reasonable effort should be made to conduct all protocol-required procedures to complete the study. Patients may be removed from the study for the following reasons:

1. Screen Failures.
2. Withdrawal by Patient.
3. Adverse Event: Patient experiences an AE that, in the Investigator's opinion, necessitates withdrawal from the study.
4. Investigator Decision: Investigator feels it is in the patient's best interest to terminate participation for reasons other than an AE.
5. Protocol Violation: Patient is noncompliant with protocol procedures, becomes pregnant, violates study entry criteria, or starts an exclusionary concomitant medication.
6. Lost to Follow-Up: Patient fails to return for study visits and cannot be reached with reasonable, repeated attempts.
7. Administrative Reasons: The FDA or other regulatory authority discontinues the study protocol or the clinical study site discontinues participation.

Any withdrawal must be fully documented in the patient's source records. The documentation must include the reason for the withdrawal and details of any sequelae (followed until symptoms resolve or improve, as appropriate).

If a patient is withdrawn from the study, will be encouraged to complete the procedures outlined in Visits 15 and 16.

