4. STUDY PLAN AND TIMING OF PROCEDURES

[Table 1](#) presents the schedule of assessments for this study.

Table 1 Study Plan

Evaluation	Screening	Run-in	Treatment Period					End of treatment/Early Termination or Rescue ^a
			1	2	3	4	5	
Visit	1	2	3	4	5	6	7	8
Week	-2	-1	0	4	8	12	15	16
Relative to Randomization (days)	-14	-9	R	28	56	84	103	112
Visit Window (±days)	(+7)	(±4^b)	0	(±5)	(±5)	(±5)	(±5)	(±4^b)
Obtain Informed Consent	X							
Review Medical and Surgical History	X							
Review Eligibility Criteria (Inclusion/Exclusion Criteria)	X							
Review Randomization Criteria			X					
Verify Patient Fasted 10 Hours	X	X	X	X	X	X	X	X
Complete Physical Examination	X							X
Brief Physical Assessment (at the Investigator's discretion)				X	X	X	X	
Body Weight	X		X	X	X	X	X	X
Height	X							
Body Mass Index	X							X
Vital signs (reclining/standing BP and HR)	X		X	X	X	X	X	X
Waist and Hip Circumference	X		X	X	X	X		X
12-lead ECG	X							X
Review Concomitant Medications ^c	X	X	X	X	X	X	X	X
Provide Diet and Exercise Counseling	X		X		X			
Verify IP Compliance				X	X	X	X	X
Dispense Study Medication			X	X	X	X		
Provide Glucose Meter and Supplies/Instructions for 7-point SMBG		X						
Perform 7-point SMBG Prior to Site Visit			X ^d	X	X	X	X ^d	X

Evaluation	Screening	Run-in	Treatment Period					End of treatment/Early Termination or Rescue ^a
	1	2	3	4	5	6	7	8
Visit	-2	-1	0	4	8	12	15	16
Week	-14	-9	R	28	56	84	103	112
Relative to Randomization (days)	(+7)	(±4 ^b)	0	(±5)	(±5)	(±5)	(±5)	(±4 ^b)
Review 7-point SMBG and hypoglycemia episodes			X	X	X	X	X	X
Collect Glucose Meter/Unused Supplies								X
Collect unused study medication								X
Dispense Rescue Medication (if needed)					X	X	X	
Assess AEs		X	X	X	X	X	X	X
Pregnancy Test (urine and serum if urine test positive) WOCBP only	X	X	X	X	X	X	X	X
Clinical Chemistry, Hematology ^c	X				X			X
eGFR and Serum Creatinine	X	x	x	x	X	x	x	X
HbA1C	X	X		X	X	X	X	X
FPG/ketones	X	X	X	X	X	X	X	X
Fasting Serum Lipids ^f	X	X			X		X	X
Thyroid function (TSH and T4)	X							
FFA	X							X
Urinalysis ^e	X							X
Double Tracer OGTT ^h with IC		X						X
Glucose Turnover Study ⁱ			X				(X) ^j	
DEXA	X							X

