6.7.1 Maternal exposure

If a patient becomes pregnant during the course of the study, all study medication should be discontinued immediately.

Pregnancy itself is not regarded as an AE unless there is a suspicion that the IP under study may have interfered with the effectiveness of a contraceptive medication. Congenital abnormalities/birth defects and spontaneous miscarriages should be reported and handled as SAEs. Elective abortions without complications should not be handled as AEs. The outcome of all pregnancies (spontaneous miscarriage, elective termination, ectopic pregnancy, normal birth, or congenital abnormality) should be followed up and documented even if the patient was discontinued from the study.

If any pregnancy occurs in the course of the study, then the Investigator or other site personnel will inform the UTHSCSA IRB within 1 day i.e., immediately but **no later than 24 hours** of when he or she becomes aware of it.

The designated study sponsor representative will work with the Investigator to ensure that all relevant information is provided to the safety data entry site within 1 or 5 calendar days for SAEs and within 30 days for all other pregnancies.

The same timelines apply when outcome information is available.

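### For a patient who stops because of pregnancy, the protocol ends study medication but still routes her to the radiotracer tests and DEXA, and its negative-test rule names study medication only

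*Combined protocol and SAP*

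**What the plan says.** **The negative-test rule.** Section 5.2.1.4 (Pregnancy testing) states: "The first dose of study medication or any other in-clinic dose of study medication will not be administered until a negative result is obtained". Table 1 schedules the test at all eight visits, in the row "Pregnancy Test (urine and serum if urine test positive) WOCBP only".

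**What happens on pregnancy.** Section 6.7.1: "If a patient becomes pregnant during the course of the study, all study medication should be discontinued immediately". Section 3.10, under protocol violation, includes pregnancy among the reasons for removal: "Patient is noncompliant with protocol procedures, becomes pregnant, violates study entry criteria, or starts an exclusionary concomitant medication".

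**What happens to patients who stop.**
- Section 3.9.2: "Patients who discontinue from the study medication will have an Early Termination Visit equivalent to the Week 16 assessments plus a glucose turnover study".
- Table 1, footnote a, applies the early-termination procedures to every patient who terminates, including the turnover study and all Visit 8 assessments.
- Section 3.10 says a withdrawn patient "will be encouraged to complete the procedures outlined in Visits 15 and 16". Table 1 has only Visits 1 to 8, so this presumably means Weeks 15 and 16, that is Visits 7 and 8.
- Section 4.2.2 confirms that Visit 8 includes the double tracer OGTT and a DEXA scan.

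**What the tests involve.** The turnover study (Section 5.1.8) is a primed continuous tritiated-glucose infusion, and footnote i of Table 1 has investigational product given at Time 0 of it. The OGTT (Section 5.1.9) uses a similar infusion, and in addition "patients will receive 75 grams of glucose containing 100" µCi of carbon-14 glucose by mouth.

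**The concern.** Two things stand out.

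First, the instructions for a patient who stops because of pregnancy do not fit together. One set ends her treatment. Another, written for early terminators in general, sends her to two radiotracer tests and an X-ray scan. A third puts a tablet inside one of those tests. None of these sections mentions pregnancy as an exception.

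Second, the only rule that waits for a negative pregnancy test is worded for study medication. The tracer infusion, the labelled drink and DEXA are not mentioned, although some of them precede the tablet or occur with no tablet at all.

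At stake is the safety of a small number of participants. A site that follows the mandatory wording literally would expose a pregnant patient to tracer and X-ray for end-of-treatment measurements that do not enter the primary analysis. A site that does not follow it has no text to rely on.

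**Working it through.** The point is textual. The plan gives no figure to reproduce; the arithmetic only sizes the exposure.

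**Step 1: the route after a positive test on treatment**

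| Place | Instruction | Strength | Pregnancy exception |
|---|---|---|---|
| 6.7.1 | Stop all study medication | Immediate | Is the pregnancy rule |
| 3.10 | Pregnancy is a reason for removal | Permissive | Names pregnancy |
| 3.9.2 | Week 16 assessments plus turnover study for those who stop medication | Mandatory | None |
| Table 1, footnote a | Early-termination procedures for all who terminate | Mandatory | None |
| 3.10, last sentence | Complete end-of-study procedures | Encouraged | None |
| Table 1, footnote i | Investigational product at Time 0 of turnover study | Mandatory | None |
| 5.2.1.4 | No in-clinic dose until the test is negative | Mandatory | Is the negative-test rule |

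Sections 6.7.1 and 3.9.2 together lead to the turnover study. Footnote i then calls for a tablet that 5.2.1.4 and 6.7.1 bar, so for this patient the turnover study cannot be run as specified.

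**Step 2: what the negative-test rule reaches**

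- Visits 3 and 7: tritium starts at -180 minutes and the tablet is given at Time 0. The rule on the tablet can be met after three hours of infusion.
- Visits 2 and 8: the OGTT text contains no tablet.
- Visit 1: DEXA is done before any study dose.
- Visit 3: Section 4.1.3 has a confirmatory serum sample drawn before the turnover study if the urine test is positive, but does not say that the result must be awaited.

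Before randomization, tracer and DEXA are therefore not made conditional on a negative result, but neither are they ordered for a pregnant woman. She fails Section 3.1 and exclusion 29 in Section 3.2, and Section 3.4 requires withdrawal of enrolled patients found ineligible.

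**Step 3: administered activity**

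Inputs from Sections 5.1.8 and 5.1.9: prime = 25 µCi × FPG/100, capped at 50 µCi; infusion 0.25 µCi/min; turnover study from -180 to 300 minutes (480 minutes); OGTT from -180 to 240 minutes (420 minutes). The FPG unit in the prime formula is not stated; I assume mg/dL and show FPG 120 up to 200, where the cap is reached.

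| | FPG 120 | FPG 200 or more |
|---|---|---|
| Prime | 30 | 50 |
| Tritium by Time 0 of turnover study: prime + 0.25 × 180 | 75 | 95 |
| Turnover total: prime + 0.25 × 480 | 150 | 170 |
| OGTT tritium: prime + 0.25 × 420 | 135 | 155 |
| Both tests, tritium (µCi) | 285 | 325 |
| OGTT carbon-14 (µCi) | 100 | 100 |

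In the turnover study, 75/150 = 50% to 95/170 = 56% of the tritium is given before the tablet to which the negative-test rule applies.

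**The case against.** The strongest reply is that the mandatory sentences in Section 3.9.2 and footnote a are generic early-termination text, while pregnancy is handled separately in Sections 6.7.1 and 3.10, and 3.10 only encourages the procedures. Patients may decline, contraception is required of women of childbearing potential, and Section 1.3.1 calls the radioactivity low and unlikely to harm study patients. An investigator would probably use judgment.

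Part of this stands. Section 3.10 is soft, and the event should be rare. But 3.9.2 covers anyone who stops study medication, which is exactly what 6.7.1 makes this patient do. Section 1.3.1 does not address a fetus. Relying on judgment here means relying on staff to depart from a mandatory sentence.

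Some stronger readings are tempting but unsupported:
- *That the plan contradicts its own reason for excluding pregnant women.* Section 1.2 gives unknown drug risk as the reason, not radiation.
- *That Visit 8 or early termination is when a pregnancy would be found.* Tests run at every visit, and Section 3.8 tells women to report suspected pregnancy immediately. A patient first positive at Visit 8 has normally had her turnover study at Visit 7, so only the OGTT and DEXA remain and the 325 µCi total does not describe her.
- *That exposure of pregnant women at Visits 1 to 3 is directed.* A positive test makes them ineligible.
- *That the plan instructs re-dosing in pregnancy.* Footnote i conflicts with 5.2.1.4 and 6.7.1; it does not override them.

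**Conclusion.** The point holds in a limited form. For a patient who stops because of pregnancy, Sections 3.9.2, 3.10, 5.2.1.4, 6.7.1 and footnotes a and i of Table 1 cannot all be followed, and the mandatory early-termination wording leads to tracer and X-ray procedures without an exception. Separately, the negative-test rule is silent on those procedures at every visit; before randomization that is a gap, not an instruction.

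If both tracer tests were completed, the administered activity would be at most 325 µCi of tritium and 100 µCi of carbon-14, with one DEXA. This assumes the capped prime on both days and a turnover study run to its full length. It does not estimate fetal dose or harm, which the documents do not allow. The number of cases should be very small.

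The conclusion concerns the protocol text as supplied. The consent pages were removed and the text of Appendices B and C is not included; either might contain relevant wording. The point is worth correcting because following the stated rules gives a worse safety result than the plan appears to intend.

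**What to change.** The sponsor and investigator should reconcile Sections 3.9.2, 3.10, 5.2.1.4 and 6.7.1 and footnotes a and i of Table 1, so that the text states:

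1. how the early-termination procedures apply to a patient who stops because of pregnancy, including the dose that footnote i places in the turnover study;
2. how the pregnancy test already scheduled at each visit relates to the start of the tracer infusion, the labelled glucose drink and DEXA.

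No clinical rule is proposed here; the choice belongs to the sponsor and investigator. Two small inconsistencies can be settled in the same edit: Section 3.10 refers to visit numbers that do not exist in Table 1, and Section 5.2.1.4 tests all women without a hysterectomy while Table 1 tests only women of childbearing potential.

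The cost is a few sentences and no new test. Depending on what is decided, end-of-treatment EGP may be missing for a rare patient. Section 8.5.1 already leaves early terminators out of the primary analysis, and Section 3.3.1 replaces randomized patients who discontinue early, so the primary comparison loses nothing it would otherwise have used.
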